11.4. Analysis populations

OPTIMISE_Protocol_V5.0_17Jun2022.docx Clinical Research Protocol Template version 15.0 © Copyright: The University of Oxford and Oxford University Hospitals NHS Foundation Trust 2019 All participants will be included as randomised (intention to treat) analysis.

11.5. Decision points

No formal comparative interim analysis will be undertaken but an independent Data and Safety Monitoring Committee will review accruing data, conduct and safety and will undertake a blinded review of the assumptions used in the sample size calculation approximately half-way through the study.

11.6. Stopping rules

There are no planned stopping rules.

11.7. The Level of Statistical Significance

The level of significance to be used is 0.05.

11.8. Procedure for Accounting for Missing, Unused, and Spurious Data.

It is intended that analysis will be on complete cases, but the nature and pattern of missingness will be carefully considered and documented, in particular as to whether the data can be treated as missing at random. If missing data is severe or it is judged appropriate, missing data will be imputed using various assumptions for missing data mechanisms to check the sensitivity of the primary analysis. Reasons for ineligibility, non-compliance, withdrawal or other protocol violations will be documented.

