9.10. Early Discontinuation/Withdrawal of Participants

During the course of the study a participant may choose to withdraw early from the study treatment at any time. This may happen for several reasons, including but not limited to:

- The occurrence of what the participant perceives as an intolerable AE.
- Inability to comply with study procedures
- Participant decision

Participants may choose to stop treatment and/or study assessments but may remain on study followup. Participants may also withdraw their consent, meaning that they wish to withdraw from the study completely.

According to the design of the study, participants may have the following two options for withdrawal;

- 1) Participants may withdraw from active follow-up and further communication but allow the study team to continue to access their medical records and any relevant hospital data that is recorded as part of routine standard of care.
- 2) Participants can withdraw from the study but permit data and samples obtained up until the point of withdrawal to be retained for use in the study analysis. No further data or samples would be collected after withdrawal.

In addition, the Investigator may discontinue a participant from the study treatment at any time if the Investigator considers it necessary for any reason including, but not limited to:

- Adverse Event
- Pregnancy
- Ineligibility (either arising during the study or retrospectively having been overlooked at screening)
- Significant protocol deviation
- Significant non-compliance with treatment regimen or study requirements
- Clinical decision

OPTIMISE_Protocol_V5.0_17Jun2022.docx Clinical Research Protocol Template version 15.0 © Copyright: The University of Oxford and Oxford University Hospitals NHS Foundation Trust 2019 If participants withdraw/are withdrawn from treatment, then standard follow up in NHS clinics will be used to ensure safety but no further study visits would be required.

Wherever possible the data of randomised participants should be analysed. Withdrawal from the study treatment will not result in exclusion of the data for that participant from certain analyses. Participants will not be replaced. The type of withdrawal and reason for withdrawal (if known) will be recorded in the CRF.

If the participant is withdrawn due to an adverse event, the Investigator will arrange for follow-up at clinic visits or by telephone calls until the adverse event has resolved or stabilised.

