Sites are reminded that if a patient withdraws/is withdrawn from treatment, it is not necessary for the participant to be withdrawn from future study follow up, unless this is necessary (i.e participants requests, or due to non-attendance).

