11.2. Description of the Statistical Methods

The primary clinical response outcome will be the achievement of the MDA criteria. This is a dichotomous composite criteria including clinical outcomes (tender joint count, swollen joint count, enthesitis count and psoriasis score) and patient reported outcomes (patient global score, patient pain score and function measured by the HAQ. To be classified as being in MDA, patients must achieve 5 or more of the criteria given below:

Domain	Measure Used	Criteria for assessing MDA
Peripheral arthritis	Tender joint count (68)	≤1
Peripheral arthritis	Swollen joint count (66)	≤1
Enthesitis	Enthesitis count (LEI and SPARCC)	≤1
Psoriasis	PASI	≤1
Pain	Patient pain VAS	≤15mm
Global disease activity	Patient global VAS	≤20mm
Function	HAQ	≤0.5

The proportion of patients achieving the criteria in the Th17 high vs Th17 low groups will be compared within treatment arms. Primary analysis will be logistic regression adjusted for Th17 as a binary indicator, treatment and an interaction between the 2. We will also adjust for the stratification factors study centre and psoriasis severity. A random effect will be included to account for any heterogeneity in the response due to recruitment centre, with the other variables being incorporated as fixed effects. Primary focus is on the interaction between biomarker and treatment, we will report the p-value for this

OPTIMISE_Protocol_V5.0_17Jun2022.docx

Clinical Research Protocol Template version 15.0

© Copyright: The University of Oxford and Oxford University Hospitals NHS Foundation Trust 2019

interaction and consider a p-value < 0.05 as significant. We will report the mean response rate by treatment and also for each of the 4 strata defined by treatment and biomarker along with 95% CI. Analysis will be on an intention to treat basis, that is according to group randomised to irrespective of compliance with treatment allocation.

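### Patients who stop treatment can lack a week-24 MDA and then fall out of a complete-case primary analysis that section 11.4 says includes everyone randomised

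*Protocol*

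**What the plan says.** Five statements in the protocol bear on this.

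- Section 11.2 (statistical methods): "Analysis will be on an intention to treat basis, that is according to group randomised to irrespective of compliance with treatment allocation".
- Section 11.4 (analysis populations): "All participants will be included as randomised (intention to treat) analysis".
- Section 11.8 (missing data): "It is intended that analysis will be on complete cases". Imputation is conditional: "If missing data is severe or it is judged appropriate, missing data will be imputed". Its stated purpose is to check how sensitive the primary analysis is.
- Section 9.10 (withdrawal), on patients who leave treatment: "standard follow up in NHS clinics will be used to ensure safety but no further study visits would be required".
- Section 9.10 also points the other way. "Participants may choose to stop treatment and/or study assessments but may remain on study followup", and sites are reminded that after withdrawal from treatment "it is not necessary for the participant to be withdrawn from future study follow up".

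No section says how a randomised participant without a week-24 MDA is classified. Section 11.3 allows 10% loss to follow-up, and its power table uses 388 of the 424 randomised, so some non-completers are expected.

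**The concern.** The primary endpoint is a binary MDA status at week 24. Section 9.10 gives sites two messages about patients who stop treatment: they need no more study visits, and they need not leave follow-up. No text requires the week-24 assessment once treatment has stopped. A site that follows the first message loses the endpoint, and section 11.8 then drops the patient.

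Stopping for intolerance or by clinical decision plausibly goes with not reaching MDA, so this missingness may be related to outcome. Three outputs are exposed: the response rates by arm and in the four strata (section 11.2), the modelled outcomes of a precision-medicine pathway (section 11.2, phase 2) and, under a narrower condition, the primary interaction test.

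**Working it through.** **Inputs from section 11.3.** MDA rates for Th17 low/high are 60%/40% on TNFi and 40%/60% on IL-17Ai; about 106 per cell; two-sided 5%; 10% loss. The 60% cells are called matched below and the 40% cells mismatched. The protocol does not say how losses split between cells, so every split below is an assumption.

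**Reproducing the plan's power.** The check is a Wald test of the interaction log odds ratio, without centre or psoriasis terms.

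- Log ratio of odds ratios = 2 × [logit(0.6) − logit(0.4)] = 2 × 0.811 = 1.622; ratio = 5.06.
- With 97 per cell (388/4): SE = √[4/(97 × 0.24)] = 0.4145; z = 3.91; power 97.5%, or 97.7% by simulation. The protocol states 98.06%.
- The smaller-interaction row (IL-17Ai 0.4/0.6, TNFi 0.55/0.45) simulates at 83.9% against 83.68% stated.
- With all 106 per cell the main scenario has 98.3% power.

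**Effect of losing non-responders.** Let p be the true rate in a cell and m the share of its non-responders with no week-24 MDA. Responders are assumed complete.

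- Observed rate = p / [p + (1 − p)(1 − m)].
- Observed log odds = logit(p) − ln(1 − m).

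The interaction therefore shifts only through the interaction contrast of ln(1 − m). If 1 − m is an arm factor times a biomarker factor, that contrast is zero and the ratio is unbiased. Otherwise, with one m for mismatched and one for matched cells, observed ratio = 5.06 × [(1 − m_mis)/(1 − m_mat)]².

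**Scenario A: m = 20% in every cell.**
- Patients lost: 0.20 × 60% = 12% in mismatched cells, 0.20 × 40% = 8% in matched cells, 10% overall.
- Rates: 0.40/0.88 = 45.5% and 0.60/0.92 = 65.2%, each about 5 points too high.
- Ratio unchanged at 5.06; power 97.1% (97.6% simulated).

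**Scenario B: m = 25% mismatched, 10% matched.**
- Patients lost: 15% and 4%, 9.5% overall, inside the planned 10%.
- Rates: 0.40/0.85 = 47.1% and 0.60/0.96 = 62.5%.
- Ratio: 5.06 × (0.75/0.90)² = 3.52; log ratio 1.257.
- SE = √{2 × [1/(90.1 × 0.471 × 0.529) + 1/(101.8 × 0.625 × 0.375)]} = 0.416; z = 3.02; power about 86%.
- In the smaller-interaction row the same losses leave about 54% power, against 87% with everyone observed.

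**Scenario C: m = 30% mismatched, 10% matched.** Ratio 5.06 × (0.70/0.90)² = 3.06; power about 76%. Overall loss is (18% + 4%)/2 = 11%, just above the planned allowance.

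**Scenario D: loss differs by arm only.** With a true 50% in both arms, m = 20% on TNFi and 10% on IL-17Ai gives 0.50/0.90 = 55.6% against 0.50/0.95 = 52.6%, a spurious 2.9-point drug difference. The interaction is untouched.

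**Scenario E: no true interaction, all cells 50%, m = 30% in two diagonal cells and 10% in the other two (10% overall).** A false log ratio of 2 × ln(0.70/0.90) = −0.50 appears, and the type I error is about 23%.

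**Does analysing everyone cost power?** Take all 424, count anyone missing as a non-responder, and let the design rates hold among completers. At 10% loss, simulated power is 96.2% in the main scenario and 79.9% in the smaller-interaction row. Complete-case analysis with loss at random gives 97.4% and 83.1%.

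**The case against.** The strongest reply is that the text permits this loss and does not impose it. Section 9.10 allows follow-up to continue after treatment stops, keeps the data of those who stop, and asks that randomised participants' data be analysed where possible. The week-24 visit coincides with routine care, so a patient who stops but attends stays in the analysis. Section 11.8 has the missingness examined and foresees imputation under several mechanisms. Section 11.2 defines intention to treat by grouping, that is, "according to group randomised to irrespective of compliance with treatment allocation", which a complete-case analysis by randomised arm can satisfy. All of this stands. A reader might infer that treatment failures will drop out; the documents support only that they can. Stopping is also not the same as failing MDA, since section 9.10 lists pregnancy, ineligibility and participant choice among the reasons.

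A second tempting inference is that the trial's own hypothesis predicts a biased interaction, because failures, and so losses, would be commoner in mismatched cells. Scenario A shows otherwise: losses are 12% against 8% and the ratio does not move. The hypothesis predicts more non-responders in those cells, not that each one is likelier to be lost. Site staff do not see the immunophenotype result, so knowledge of the biomarker cannot drive stopping. An uneven share lost remains possible, for example if non-response is more marked in mismatched cells, but nothing in the documents shows it.

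The objection does not remove the conflict between sections 11.4 and 11.8, the mixed message in section 9.10, or the lack of any rule for a missing MDA. The SAP was not among the documents reviewed and may add detail, but the complete-case intention is stated in the protocol itself.

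**Conclusion.** The point holds as an internal conflict with a plausible route to bias. Sections 9.10, 11.2, 11.4 and 11.8 do not together say who must have a week-24 MDA or what happens to those who do not.

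- **Response rates and modelled pathway benefit:** inflated if the missing are mainly non-responders, by about 5 points at the planned 10% loss.
- **Primary interaction:** unbiased if the share of non-responders lost is constant, or varies by arm or by biomarker alone (multiplicatively on the share retained). It is biased if that share varies by cell beyond this. The fall from 5.06 to 3.52, with power going from about 98% to 86%, rests on an assumed 25%/10% split.
- **Drug comparison:** a difference in loss by arm can distort the rates reported by treatment, but section 11.3 says the treatment effect itself is not of interest, so this is secondary.

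The documents do not support a claim that the primary test is invalid or that failures are systematically removed.

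**What to change.** 1. **Section 9.10:** reconcile the two messages. State that the week-24 MDA assessment is sought from every participant who has not withdrawn from follow-up, whether or not still on treatment. This concerns outcome collection only and leaves treatment decisions as they are.
2. **Section 11.8, aligned with 11.2 and 11.4:** replace complete cases as the sole primary approach with a pre-specified analysis of all randomised participants. Multiple imputation from arm, Th17 group, baseline and week 12/16 data is one suitable choice among several; the imputation model should include the arm-by-Th17 interaction.
3. **Partly missing MDA:** score it when the observed items already decide it. Under the 5-of-7 rule, that means 5 met or 3 failed.
4. **Sensitivity analyses:** make them unconditional, and include missing counted as non-response and complete cases.

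The cost is revised wording, modest extra analysis and possibly slightly lower reported response rates. The visit is already scheduled. Power is not a barrier: even with every missing patient counted as a failure, it stays at about 96% in the main scenario at 10% loss. The wording on visits is the more urgent part, because a week-24 assessment that was not made cannot be recovered at analysis.

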11.9. Procedures for Reporting any Deviation(s) from the Original Statistical Plan

Any deviation(s) from the original statistical plan will be described and justified in the protocol and/or in and updated statistical analysis plan and/or the final report, depending on the timing of the changes.

11.10. Health Economics Analysis

Not applicable.

12. DATA MANAGEMENT

The data management aspects of the study are summarised here with details fully described in the Data Management Plan.

12.1. Source Data

Source documents are where data are first recorded, and from which participants' CRF data are obtained. These include, but are not limited to, hospital records (from which medical history and previous and concurrent medication may be summarised into the CRF), clinical and office charts, laboratory and pharmacy records, diaries, microfiches, radiographs, and correspondence.

CRF entries will be considered source data if the CRF is the site of the original recording (e.g. there is no other written or electronic record of data). For this study the following data are expected to be captured directly on the CRFs thus are considered source documents:

OPTIMISE_Protocol_V5.0_17Jun2022.docx Clinical Research Protocol Template version 15.0 © Copyright: The University of Oxford and Oxford University Hospitals NHS Foundation Trust 2019

Page 32 of 43

• Patient reported questionnaires

Source data will also be generated through the analysis of the blood samples for study purposes.

All documents will be stored safely in confidential conditions. On all study-specific documents, other than the signed consent form, the participant will be referred to by the study participant number/code and initials, not by name.

12.2. Access to Data

Direct access will be granted to authorised representatives from the Sponsor and host institution for monitoring and/or audit of the study to ensure compliance with regulations.

12.3. Data Recording and Record Keeping

The results of the composite clinical outcome measures will be recorded in the patients' medical notes and will be extracted by a study investigator and entered into an eCRF. The routine clinical blood samples will be processed at the clinical site laboratory and the results entered into the eCRF by the participating site.

The participants will be identified by a unique trial specific number in any database. The name and any other identifying detail will NOT be included in any trial data electronic file.

All paper documents containing personal data (e.g. informed consent forms) will be stored securely and only accessible by study staff and authorised personnel. The study investigator is responsible for keeping these documents securely to ensure that in case of an emergency, participants can be identified and contacted. The code list will be kept for the archive period as specified in section 20.

All study data will be stored for five years after the end of the study. To meet HTA traceability requirements consent forms for those participants who provide consent to the long term storage and future use of samples will be retained until the sample is depleted or destroyed.

During and/or after the end of the study a de-identified study dataset will be created and stored for as long as it is useful, and may be shared with the NIHR (funder) and other researchers upon request and/or uploaded into a research data repository. Sharing and storage of this data will continue for as long as this data is useful.

A data management plan for the study will be written in line with OCTRU SOP requirements.

13. QUALITY ASSURANCE PROCEDURES

This study will be coordinated by the UKCRC registered Oxford Clinical Trials Research Unit (OCTRU) at the University of Oxford. The study may be monitored, or audited in accordance with the current approved protocol, GCP, relevant regulations and standard operating procedures.

13.1. Risk assessment

A risk assessment and monitoring plan will be prepared before the study opens and will be reviewed as necessary over the course of the study to reflect significant changes to the protocol or outcomes of monitoring activities.

13.2. Study monitoring

Regular monitoring will be performed according to the study specific Monitoring Plan to verify that the clinical study is conducted and data are generated, documented and reported in compliance with the protocol, the principles of GCP and the applicable regulatory requirements.

13.3. Study Committees

13.3.1. Trial Management Group

The Trial Management Group (TMG) will consist of the core study team, relevant CTU members, the Chief Investigator and grant co-applicants.

The TMG will be responsible for running the study and will meet, usually on a monthly basis, to report on progress and ensure milestones are met. The TMG will be responsible for the close monitoring of recruitment and the decision to increase the number of participating sites, with a formal review of this occurring 6 months after the start of recruitment. A Charter or Terms of Reference will be put in place according to OCTRU SOPs.

13.3.2. Data and Safety Monitoring Committee

The Data and Safety Monitoring Committee (DSMC) will monitor accruing data, study conduct and safety of the participants. The DSMC will also undertake a blinded interim review of the data to ensure that the assumed response rates overall are as expected. The DSMC will meet at least annually during the recruitment period.

A DSMC Charter will describes the membership, remit and responsibilities of this committee.

13.3.3. Trial Steering Committee

The Trial Steering Committee (TSC) will be comprised of independent clinicians, statisticians, health service researchers, and lay patient representatives. The TSC will monitor the study's progress and safety and will provide independent advice.

The TSC will meet 6 months after the start of recruitment then at least every 12 months subsequent to that during the recruitment period.

A TSC Charter will describe the membership, remit and responsibilities of this committee.

14. PROTOCOL DEVIATIONS

A study related deviation is a departure from the ethically approved study protocol or other study document or process (e.g. consent process or administration of study intervention) or from the principles

Page 34 of 43

of Good Clinical Practice (GCP) or any applicable regulatory requirements. Any deviations from the protocol will be documented and reported to the Coordinating Trial Office.

OCTRU standard operating procedures will be in place describing the procedure for identifying noncompliances, escalation to the trial management team and assessment of whether a non-compliance /deviation may be a potential Serious Breach.

15. SERIOUS BREACHES

A "serious breach" is a breach of the protocol or of the conditions or principles of Good Clinical Practice which is likely to affect to a significant degree –

- (a) the safety or physical or mental integrity of the trial subjects; or
- (b) the scientific value of the research.

In the event that a serious breach is suspected the Sponsor must be contacted within 1 working day. In collaboration with the C.I., the serious breach will be reviewed by the Sponsor and, if appropriate, the Sponsor will report it to the approving REC committee and the relevant NHS host organisation within seven calendar days.

Any site staff who become aware of a potential serious breach must report this to the coordinating trial office as soon as possible. The trial team at the coordinating trial office will then liaise as the Sponsor and CI as required.

16. ETHICAL AND REGULATORY CONSIDERATIONS

16.1. Compliance

The trial will be conducted in compliance with the approved protocol and standard operating procedures (SOPs), the Declaration of Helsinki, the principles of Good Clinical Practice (GCP), the UK Data Protection Act and all other applicable regulatory and governance frameworks including the UK policy framework for health and social care research.

16.2. Approvals

Following Sponsor approval the protocol, informed consent form, participant information sheet will be submitted to an appropriate Research Ethics Committee (REC), and HRA (where required) and host institutions for written approval.

The Investigator will submit and, where necessary, obtain approval from the above parties for all substantial amendments to the original approved documents.

16.3. Other Ethical Considerations

A small number of the questions in the participant questionnaires may be upsetting to some participants. As participants will be completing the questionnaires during their outpatient appointments their clinical

OPTIMISE_Protocol_V5.0_17Jun2022.docx Clinical Research Protocol Template version 15.0 © Copyright: The University of Oxford and Oxford University Hospitals NHS Foundation Trust 2019

Page 35 of 43

and/or research team will be present and able to support them should this occur. If anything of clinical significance is identified, the clinical team will be notified.

